- For summaries at a patient level, all values should be included, regardless of whether they appear in a corresponding visit based summary, when deriving a patient level statistic such as a maximum.
- Baseline will be defined as the last non-missing measurement prior to dosing with study treatment (excluding unscheduled visit). For the re-treatment period for immunotherapy agents then baseline is similarly defined as the last non-missing measurement prior to the first dose on the re-treatment period. For laboratory data, any assessments made on day 1 will be considered pre-dose. Alternatively, if two visits are equally eligible to assess patient status at baseline (e.g., screening and baseline assessments both on the same date prior to first dose with no washout or other intervention in the screening period), the average can be taken as a baseline value. For non-numeric laboratory tests (ie some of the urinalysis parameters) where taking an average is not possible then the best value would be taken as baseline as this is the most conservative. In the scenario where there are two assessments on day 1, one with time recorded and the other without time recorded, the one with time recorded would be selected as baseline. Where safety data are summarised over time, study day will be calculated in relation to date of first treatment.
- Missing safety data will generally not be imputed. However, safety assessment values of the form of "< x" (i.e., below the lower limit of quantification) or > x (i.e., above the upper limit of quantification) will be imputed as "x" in the calculation of summary statistics but displayed as "< x" or "> x" in the listings.
- For missing diagnostic dates, if day and/or month are missing use 01 and/or Jan. If year is missing, put the complete date to missing.
- For missing concomitant medication and AE start dates:
 - If year is missing (or completely missing), do not impute.

- If year is present and months and day are missing; or year and day are present and month is missing, impute as January 1st.
- If year and month are present and day is missing, impute day as first day of the month.
- For missing concomitant medications and AE end dates, the following will be applied:
 - If year is missing (or completely missing), do not impute.
 - If year is present and month and day are missing; or year and day are present and month is missing, impute as December 31st.

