 - If year and month are present and day is missing, impute day as last day of the month.
 - When the patient has died in the same month/year of partial stop date, use date of death.
- For medications, a conservative approach will be followed and events will be assumed to be concomitant unless the end date is before the first dose of IP. If the start and end dates are both missing it is considered concomitant.
- In addition for AEs if, for a partial start date, the AE start date could (when also considering the AE end date) potentially be on the first study treatment date, the AE start date will be imputed with the first study treatment date to assume a "worst case" scenario; e.g. AE from UNK-Jun-2017 to 23-Jul-2017 with the first study treatment date 21-Jun-2017, then the AE start date will be imputed to 21-Jun-2017.

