4. ANALYSIS METHODS

4.1 General principles

No hypothesis testing is planned for this single arm study. Each module will be summarised separately.

The general principles as mentioned below will be followed throughout the study:

- Descriptive statistics will be used for all variables, as appropriate, and will be presented separately for each module. Descriptive safety and efficacy data from the STRONG study may be utilized as supporting evidence for health authority considerations.
- Continuous variables will be summarized by the number of observations, mean, standard
 deviation, median, minimum, and maximum. For log transformed data it is more
 appropriate to present geometric mean, coefficient of variation (CV), median, minimum
 and maximum. Categorical variables will be summarized by frequency counts and
 percentages for each category.
- Unless otherwise stated, percentages will be calculated out of the population total.
- Exact CIs for proportions will be calculated using the Clopper-Pearson method.
- For percentiles of survival times based on the Kaplan-Meier method (eg, median survival), CIs will be calculated using the default method available in the SAS LIFETEST procedure (ie, the Klein and Moeschberger extension of the Brookmeyer-Crowley method).
- For point-estimates of survival based on the Kaplan-Meier method (eg, for OS at 12 months), CIs will be calculated using the default method available in the SAS LIFETEST procedure (ie, using Greenwood's estimate of standard error and a log-log transformation).
- For continuous data the mean and median will be rounded to 1 additional decimal place compared to the original data. The standard deviation will be rounded to 2 additional decimal places compared to the original data. Minimum and maximum will be displayed with the same accuracy as the original data.
- For categorical data, percentages will be rounded to 1 decimal place.
- SAS® version 9.3 or higher will be used for all analyses.

Baseline will be the last assessment of the variable under consideration prior to the intake of the first dose of study treatment.

All data collected will be listed.

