- At least one treatment-emergent serious AESI
- At least one treatment-emergent AESI by maximum NCI CTCAE grade
- At least one treatment-emergent AESI causally related to study medication
- At least one treatment-emergent AESI with fatal outcome
- At least one treatment-emergent AESI which required additional treatment with steroids, immunosuppressants and hormone replacement therapy
- Laboratory findings, vital signs and other safety parameters associated with AESI will be summarised as part of the AESI outcome measures.

Length of intervention with steroids, immunosuppressants and/or hormone replacement therapy for AESIs will be calculated based on treatment start and stop dates. Total treatment

times will then be combined for each patient and summarised for patients experiencing at least one treatment-emergent AESI.

The exact 95% CIs around the incidence estimates will also be reported for each AESI type.

A summary of total duration (days) of AESI will be provided. For ongoing AESI, the date of death or data cut-off will be imputed as end date.

Immuno-mediated adverse events

Summaries of treatment-emergent imAEs by AESI category and PT will include number (n) and percentage (%) of patients who have:

- At least one treatment-emergent imAE
- At least one treatment-emergent imAE by outcome
- At least one treatment-emergent imAE leading to treatment interruption or discontinuation
- At least one treatment-emergent serious imAEs
- At least one treatment-emergent imAE by maximum NCI CTCAE grade
- At least one treatment-emergent imAE causally related to study medication
- At least one treatment-emergent imAE with fatal outcome

Subgroup analyses

Subgroup analyses will be conducted for the summary of TEAEs in the following subgroups of the SS:

- Sex (male versus female)
- Age at baseline: <65 vs 65-74 vs ≥75 years of age). This will be determined from the date of birth (BRTHDAT in the DM domain) and baseline visit (VIS_DAT in the VISIT domain) on the eCRF. Patients with a partial date of birth (ie for those countries where year of birth only is given) will have an assumed date of birth of 1st Jan [given year]). Patients with a missing age value will be included using the mean age and categorised accordingly.
- Race: Asian vs non-Asian
- ECOG performance status at baseline: 0-1 vs 2
- Tumor histology: Urothelial (i.e. TCC) vs non-urothelial

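### Length of intervention for AESIs merges steroids, immunosuppressants and hormone replacement into one figure per patient and has no end-date rule for courses still ongoing

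*SAP*

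**What the plan says.** Under adverse events of special interest in SAP 4.2.1, the variable is defined in two sentences. The first is: "Length of intervention with steroids, immunosuppressants and/or hormone replacement therapy for AESIs will be calculated based on treatment start and stop dates". The second says that total treatment "times will then be combined for each patient and summarised for patients experiencing at least one treatment-emergent AESI". Neither sentence splits the result by drug class or by AESI category.

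The same subsection then plans a summary of AESI duration: "For ongoing AESI, the date of death or data cut-off will be imputed as end date". That sentence is about the event, not the drug.

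SAP 3.1.3 has the general rule for medication dates. It opens "For missing concomitant medications and AE end dates, the following will be applied" and starts with "If year is missing (or completely missing), do not impute". Death enters only for partial dates: "When the patient has died in the same month/year of partial stop date, use date of death".

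SAP 4.1 sets the statistics: "Continuous variables will be summarized by the number of observations, mean, standard" deviation, median, minimum and maximum. Kaplan-Meier estimation with censoring is planned in SAP 4.2.1 for time to event and time to resolution, but not for length of intervention.

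**The concern.** The AESI list (SAP 3.1.1.1) puts hypothyroidism, adrenal insufficiency, hypophysitis and type I diabetes beside pneumonitis, colitis and rash. Replacement for the first group may well still be running when recording stops, while a steroid course for the second group usually has an end. The documents do not give these durations, so this contrast is an assumption, but it is the situation the table has to cope with.

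Intervention/treatment is a named component of the primary objective (Protocol 2.1, SAP 1.1.1), and SAP 4.1 allows descriptive results to support health authority considerations. A single figure that depends on an unstated handling of ongoing courses, and that does not separate the classes, cannot describe how long patients needed each kind of treatment. Two programmers could follow the SAP and produce materially different tables.

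**Working it through.** The plan gives no figure for this variable, so there is none to reproduce. The check is first textual, then illustrative.

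**Step 1: look for an end date for an ongoing intervention.**
- SAP 4.2.1, intervention sentences: start and stop dates are needed; nothing is said about a course with no stop date.
- SAP 4.2.1, death or cut-off rule: applies to the AESI's own duration.
- SAP 3.1.3: a completely missing medication end date is not imputed; date of death is used only with a partial date.
- SAP 4.2.1, time to resolution: censored, but a different variable.

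No rule reaches an ongoing intervention.

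**Step 2: the possible handlings.**
- *No end date inserted.* A patient on replacement alone contributes no length. A patient with steroids and ongoing replacement contributes steroid time only, or nothing.
- *Death or data cut-off inserted.* Replacement time is added to steroid time. Protocol 7.7 and SAP 3.4.1 limit concomitant medication to 90 days after last dose, so a cut-off date counts unobserved time for anyone who stopped treatment more than 90 days earlier.

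**Step 3: effect on the planned mean.** All inputs are assumptions. Take 100 treated patients with *k* ongoing. Completed courses average *m* = 30 or 60 days, and ongoing ones average *L* of at least 180 days.

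Mean with ongoing dropped = *m*. Mean with ongoing included = [(100 − *k*)·*m* + *k*·*L*]/100. With *L* = 180, the results are lower bounds:

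| *k* | *m* = 30 | ratio | *m* = 60 | ratio |
|---|---|---|---|---|
| 20 | (2,400 + 3,600)/100 = 60 | 2.0 | (4,800 + 3,600)/100 = 84 | 1.4 |
| 40 | (1,800 + 7,200)/100 = 90 | 3.0 | (3,600 + 7,200)/100 = 108 | 1.8 |

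**Step 4: effect on the planned median.** If ongoing courses are the longest and fewer than half of patients have one, the pooled median is still a completed-course length. It is the 50/(100 − *k*) quantile of those courses: 50/80 = 62.5% for *k* = 20 and 50/60 = 83% for *k* = 40. It cannot jump to 180 days until about half are ongoing.

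**Step 5: a wider range of assumptions.** A simulation used these inputs:
- median steroid course 14, 30 or 60 days;
- 10% to 50% of treated patients on replacement that never stops, a tenth of them also on steroids;
- median survival 7 or 12 months and median AESI onset at 90 days;
- enrolment over 2.5 years;
- 1,185 days from first patient to cut-off. The synopsis dates, Q1 2017 and Q2 2020, allow 1,097 to 1,276.

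Only the calendar span and the enrolment period (2 to 3 years in the synopsis) rest on the documents. With replacement counted to death or cut-off, the pooled mean was 1.3 to 9.8 times the steroid-only mean. The pooled median was 1.1 to 1.3 times the steroid-only median at a 10% to 20% share and 1.7 to 3.1 times at 50%. With ongoing replacement left out, 9% to 45% of treated patients contributed no length.

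Within one patient, a 30-day steroid course plus 365 days of replacement gives a total that is 365/395 = 92% replacement.

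**The case against.** The strongest reply is that this is an unstated detail of a descriptive variable. The primary outcome measure is the number and proportion of patients with an AESI, no hypothesis is tested, and all data are listed. Lasting burden is also shown by AESI duration, by censored time to resolution and by prevalence plots per AESI category. That limits the consequence. But none of these outputs gives time on steroids, immunosuppressants or replacement, so the intervention component still rests on this one summary.

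A reader might infer more than the text supports:
- *That the SAP orders ongoing courses to be dropped.* It does not. SAP 3.1.3 concerns missing dates, and SAP 3.4.1 recognises ongoing as a known status and invokes the imputation rules for classifying medication as prior or concomitant. Omission is one possible handling.
- *That overlapping days are counted twice.* The SAP says times are combined, not how. Overlap is unaddressed.
- *That the count row has the same fault.* The row for "At least one treatment-emergent AESI which required additional treatment with steroids, immunosuppressants and hormone replacement therapy" stands under summaries by AESI category and preferred term, so much endocrine replacement already appears apart from steroid-treated events.
- *That the whole distribution is distorted.* Quartiles are not planned for this variable, and at low replacement shares the median moves little.

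The imAE charter (SAP Appendix 1) is not in the text available; a rule there cannot be excluded. If one exists, SAP 4.2.1 should cite it.

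**Conclusion.** The point holds. SAP 4.2.1 defines one length of intervention per patient across three drug classes and leaves ongoing courses without an end date. Either handling gives a table that cannot serve the intervention/treatment part of the primary objective: one omits open-ended replacement, the other blends it with time-limited courses.

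The size is conditional on the share of patients on ongoing replacement and on the course lengths assumed above. The sensitivity lies mainly in the mean and weakens when replacement is rare and steroid courses are long. It does not support any claim that AESI incidence or its exact intervals are wrong; those are untouched. The change is worth making because reporting by class with censoring is a better method, not merely a fuller description.

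**What to change.** In SAP 4.2.1, replace the two sentences on length of intervention with the following:
- Summarise number treated and length of intervention separately for systemic steroids, other immunosuppressants and hormone replacement, counting each calendar day once within a class.
- Report the number of patients with the intervention ongoing. Treat those courses as censored at the last medication record and use Kaplan-Meier, as for time to resolution.
- For hormone replacement, give the number started and the number ongoing as the main result.
- State that courses already running before first dose are excluded unless changed for the AESI. This is needed because exclusion criteria 17 and 18 admit patients on low-dose systemic steroids and patients with hypothyroidism stable on replacement.

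The cost is SAP wording and a few short tables in place of one. No new data collection is expected: the Table 2 footnote on concomitant medications and Protocol 7.7 already have dose, route and duration recorded for drugs used to manage AESIs. That an on-study drug can be linked to its AESI is implied there rather than stated, so the case report form should be checked.

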4.3 Follow up period

Procedures will be performed according to the Study Plan.

All patients who discontinue study treatment will attend a safety follow up visit 90 days after study treatment discontinuation.

The following procedures will be performed:

- 1. Assess AEs.
- 2. Update concomitant medications.
- 3. Record Investigator assessment of treatment response.
- 4. Record subsequent therapy.
- 5. Record survival status.

After this safety follow up visit, patients will be contacted by phone or email every 3 months to check survival status until death or final DCO, whichever occurs first.

Patients who do not discontinue treatment before the final DCO will continue to be followed after the final DCO, as indicated in Section 6.3.12.

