6.3 Recording of adverse events

6.3.1 Time period for collection of adverse events

Adverse events and SAEs will be collected from time of the patient signing the ICF until the follow up period is completed (90 days after the last study treatment administration). If an event that starts post the defined safety follow up period noted above is considered to be due to a late onset toxicity to study drug then it should be reported as an AE or SAE as applicable.

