6.3.2 Follow up of unresolved adverse events

During the course of the study, all AEs and SAEs should be proactively followed up for each patient for as long as the event is ongoing. Every effort should be made to obtain a resolution for all events, even if the events continue after the patient has discontinued study drug or the study has completed.

Any AEs that are unresolved at the patient's last visit in the study are followed up by the Investigator for as long as medically indicated, but without further recording in the CRF. AstraZeneca retains the right to request additional information for any patient with ongoing AE(s)/SAE(s) at the end of the study, if judged necessary.

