- PDL1: high >=25% vs low <25%. If data is available from the central laboratory, the central laboratory result will be used in the group derivation, otherwise, the local test result will be used.

Subgroup analyses will also be conducted for the summary of OS, ORR and DCR in the following subgroups of the SS:

- Age at baseline: <65 vs 65-74 vs ≥ 75 years of age
- ECOG performance status at baseline: 0-1 vs 2
- Primary tumor location: Bladder vs Renal pelvis and Ureter vs Urethra vs Other
- Stage: III vs IV
- Tumor histology: Urothelial (i.e. TCC) vs non-urothelial
- Previous platinum chemotherapy: platinum vs non-platinum chemotherapy
- Best response to previous therapy (CR vs PR vs SD vs PD)

- Baseline metastases: liver (+/- other visceral or non-visceral metastases) vs lymph node metastases only
- PDL1: high \geq 25% vs low \leq 25%

No formal comparisons will be performed between the subgroups.

Time-to-event analyses

Time-to-event of AESI and imAE:

Time-to-onset of AESI/imAE (by AESI/imAE category) and time-to-intervention with steroids, immunosuppressants and/or hormone replacement therapy to treat an AESI/imAE will be defined as time from first dose of durvalumab +/- tremelimumab to first onset of the event.

Time-to-event (TTE) is defined in months as follows:

TTE (months) = (Date of event or censoring–Date first dose of durvalumab [durvalumab + tremelimumab for the combinations modules]+1)/(365.25/12)

Time-to-resolution (TTR) of an AESI/imAE type is defined as the time from the first onset of an AESI/imAE type to the resolution of the AESI/imAE type. TTR is defined in months as follows:

TTR (months) = (Date of AESI/imAE resolution or censoring–Date of AESI/imAE onset+1)/(365.25/12)

Analysis of TTR will only include patients who have experienced an AESI/imAE.

The distribution of TTE and TTR times will be estimated using the Kaplan-Meier method (Kaplan and Meier 1958) and summarised using the median, twenty-fifth and seventy-fifth percentiles. TTE and TTR of imAE of NCI CTCAE grade >=3 will also be produced.

Deaths

A summary of deaths will present number (n) and percentage (%) of patients for the following categories:

- Total number of deaths (including deaths occurring within 90 days after last dose of study medication and deaths occurring after the 90 days post dosing window)

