- Death related to disease under investigation ONLY, as determined by investigator (including deaths occurring within 90 days after last dose of study medication and deaths occurring after the 90 days post dosing window)
- TEAEs with outcome of death ONLY
- AEs with outcome of death ONLY and onset date falling after 90 days follow-up period
- Deaths related to disease under investigation, as determined by the investigator, and with TEAE with outcome of death
- Deaths related to disease under investigation, as determined by the investigator, and with AE with outcome of death and onset date falling after 90 days follow-up period
- Deaths that occurred 90 days after last dose, and unrelated to AE (ie no AE with outcome of death) or disease under investigation

- Patients with unknown reason for death
- Other deaths

Summary of long term tolerability

To assess long term tolerability, provided that there are a sufficient number of patients with events to warrant it (\geq 10 events), prevalence plots and cumulative incidence plots will be presented for each AESI category and for any other events considered important after review of the safety data.

A prevalence plot provides information on the extent to which the events may be an ongoing burden to patients. The prevalence at time t after first dose of study treatment is calculated as the number of patients experiencing the event divided by the number of patients receiving study treatment or in safety follow-up at time t; generally, t is categorised by each day after dosing. The prevalence will be plotted over time. Multiple occurrences of the same event are considered for each patient but a patient is only counted in the numerator whilst they are experiencing one of the occurrences of the event. The raw cumulative incidence is the actual probability that a patient will have experienced their first occurrence of the event by a given time point.

Treatment exposure

The following summaries related to study treatment will be produced for the SS:

- Total exposure, actual exposure, and total number of cycles received will be summarised separately for the initial treatment phase and the re-treatment phase. For the modules with combination therapy, those summaries will be carried out once for each drug separately and once for combination separately from monotherapy.

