4.2.2 Efficacy data

Overall survival

OS will be summarised using the Kaplan-Meier method with median OS and its associated 95% confidence interval reported as well as the proportion of patients alive at 1, 2, 3, 4 and 5 years.

Objective Response Rate and Disease Control Rate

Objective response rate (ORR) and Disease control rate (DCR) at 6 and 12 months will be calculated for the SAF as the percentage of patients (%) with objective response and

controlled disease, respectively. ORR and DCR will be reported with the associated 95% exact Clopper-Pearson confidence interval.

The denominator used for ORR and DCR rates will be the number of patients with an assessment in the time period. A summary of investigator assessment (responding, stable or progressing) will be provided for those patients with an alternative method of assessment (e.g. WHO).

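### AESI durations are run on to death or data cut-off after adverse event recording has stopped, and 4- and 5-year survival is out of reach on the planned dates

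*SAP*

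**What the plan says.** **AESI duration.** SAP 4.2.1 (Adverse events of special interest) provides a summary of total duration in days and adds: "For ongoing AESI, the date of death or data cut-off will be imputed as end date". It names no statistics of its own. The general convention in SAP 4.1 is "Continuous variables will be summarized by the number of observations, mean, standard" deviation, median, minimum and maximum.

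**Adverse event recording.** Protocol 6.3.1 collects adverse events from consent "until the follow up period is completed (90 days after the last study treatment administration"). Its one extension is for new events judged to be late-onset toxicity. Under Protocol 6.3.2, events unresolved at the patient's last visit are "followed up by the Investigator for as long as medically indicated, but without further recording in the CRF". Under Protocol 4.3, after the 90-day safety visit "patients will be contacted by phone or email every 3 months to check survival status". Table 2 of the protocol marks adverse events up to the safety visit and not at the survival contacts.

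**Related SAP outputs.** The prevalence plot in 4.2.1 takes the number of patients with the event "divided by the number of patients receiving study treatment or in safety follow-up at time t". Time to resolution is a Kaplan-Meier analysis running to the "Date of AESI/imAE resolution or censoring", with no censoring date given. For adverse event end dates that are completely missing, the general rule in SAP 3.1.3 is not to impute.

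**Survival.** SAP 4.2.2 reports "the proportion of patients alive at 1, 2, 3, 4 and 5 years". Survival follow-up ends at the final DCO (Protocol 5.1; SAP 1.1.2), and patients alive then are censored at that date (SAP 3.3.1.1). The protocol synopsis estimates first enrolment in Q1 2017 and the final DCO in Q2 2020.

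**The concern.** When the 90-day visit falls before the DCO, the CRF has no planned way to capture a later resolution. The SAP nevertheless counts the event as continuing until the patient dies or the database is cut, and then summarises the result alongside durations that were observed to end. For these events the reported number reflects when the patient enrolled or died, not how long the toxicity lasted. A reader would take the table as the latter. AESI outcome is part of the primary objective, and SAP 4.1 allows descriptive data from the study to support health authority considerations, so the table may be read outside the study report.

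The second part is separate. Two of the five survival time points lie beyond the longest follow-up that the planned dates allow, so those rows cannot be informatively estimated.

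**Working it through.** **1. Check of the timetable.** The synopsis gives an overall duration of 4 to 5 years. From Q1 2017 to study end in Q2 2021 (Protocol 9.3):
- shortest: 31 Mar 2017 to 1 Apr 2021 = 1462 days; 1462/365.25 = 4.00 years
- longest: 1 Jan 2017 to 30 Jun 2021 = 1641 days; 1641/365.25 = 4.49 years

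This agrees with the plan, so the dates can be used.

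**2. Same record, different enrolment date.** Illustrative assumptions: first dose is day 1, AESI onset day 30, last dose day 60, event open at the 90-day visit, patient alive at DCO. Duration = end date − onset date + 1.

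| First dose | Onset | 90-day visit | Recorded | Reported, DCO 30 Jun 2020 | Not observed | Reported, DCO 1 Apr 2020 |
|---|---|---|---|---|---|---|
| 1 Jul 2017 | 30 Jul 2017 | 27 Nov 2017 | 121 d | 1067 d | 1067 − 121 = 946 d | 977 d |
| 1 Jan 2019 | 30 Jan 2019 | 30 May 2019 | 121 d | 518 d | 518 − 121 = 397 d | 428 d |

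The two records differ only in calendar date. If the patient is on treatment, or within 90 days of last dose, at death or DCO, the rule adds no unobserved time.

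**3. Effect on the mean.** Let *p* be the share of AESIs left open at a 90-day visit before the DCO, and *g* the mean days from that visit to death or DCO. Days added to the mean duration per event = *p* × *g*. The documents give neither, so both are assumed:
- 0.05 × 80 = 4 days
- 0.10 × 80 = 8 days
- 0.20 × 200 = 40 days
- 0.30 × 280 = 84 days
- 0.40 × 600 = 240 days

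The mean, SD and maximum are the most exposed statistics.

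**4. Survival follow-up.** First patient in Q1 2017, DCO in Q2 2020:
- shortest: 31 Mar 2017 to 1 Apr 2020 = 1097 days = 3.00 years
- longest: 1 Jan 2017 to 30 Jun 2020 = 1276 days = 3.49 years

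OS runs from first dose, so these enrolment-based figures are upper limits. No patient can reach 4 or 5 years. A 4-year estimate would need a DCO no earlier than Q1 2021 and a 5-year estimate one no earlier than Q1 2022, and then only for the first patients enrolled. At the planned study end the maximum is 4.49 years (step 1), so 5 years stays out of reach.

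For 3 years, assume uniform accrual over the planned 2 to 3 years. Share with potential follow-up of at least 3 years = (maximum follow-up − 3)/accrual period:
- first patient 1 Jan 2017, DCO 30 Jun 2020: 0.493/2 = 24.7%; 0.493/3 = 16.4%
- first patient 1 Jan 2017, DCO 1 Apr 2020 (3.247 years): 0.247/2 = 12.4%; 0.247/3 = 8.2%
- first patient 31 Mar 2017, DCO 1 Apr 2020: 0.2% and 0.1%

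**The case against.** The best defence is Protocol 6.3.2. It asks that events be followed for as long as they are ongoing, with every effort to obtain a resolution, and lets the sponsor request more information at study end. The stop on CRF recording applies at the last visit in the study, which is not defined. That stands as a caveat, and some end dates may be obtained. But everything after the 90-day visit is a phone call or email for survival, so that visit is the natural reading, and no routine recording of resolution is planned after it.

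The SAP also offers other views: AESIs by outcome, listings, and a censored time to resolution. These help, but time to resolution has no stated censoring date. If the DCO were used, the same unobserved time would count as time without resolution.

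The size is assumed. The 4-to-240-day range is wide, and the 1067-day case needs early discontinuation followed by long survival. Total duration might also be calculated per patient and not per event. All of this is fair: the example shows how the rule behaves, not its average effect. Nor does the SAP say that the imputed end date enters the prevalence plot; the plot matters here only because it shows the observation window the SAP itself recognises.

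Cutting at the last assessment understates events that persist, such as those needing hormone replacement. That is true, and it is why these values should be treated as censored. Late-onset events starting beyond 90 days are not a difficulty, because they fall outside the treatment-emergent AESI summaries.

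On survival, the dates are estimates and Protocol 9.3 leaves the definition of final DCO to the modules. The conclusion is therefore conditional on the planned dates.

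**Conclusion.** Both parts hold. Followed as written, the duration rule adds unobserved time to every AESI left open at a 90-day visit that precedes death or DCO. In the worked example, 121 recorded days become 1067 or 518 depending only on the date of first dose. The average effect cannot be derived from the documents. This rests on reading the last visit as the 90-day visit. The number and proportion of patients with an AESI are not affected; the duration table is supporting description, which is why this should be corrected but does not threaten the primary result.

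On the planned dates, no patient is at risk at 4 or 5 years. Three-year survival would rest on at most about a quarter of patients, and on almost none if the first patient entered at the end of Q1 2017 and the DCO fell at the start of Q2 2020.

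**What to change.** **SAP 4.2.1**
- For ongoing AESIs, replace the imputed end date with the earliest of death, DCO and last recorded adverse event assessment (normally at latest the 90-day visit), and treat the duration as censored.
- Name the same date as the censoring date for time to resolution. Censor deaths before resolution there and show their number.
- Report how many AESIs were ongoing at last assessment.
- If the total-duration table is kept, label it as recorded duration and show how many values are censored.
- State that a death or DCO end date is not carried into the prevalence numerator.

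**SAP 4.2.2**
- Remove the 4- and 5-year survival proportions unless the final DCO moves late enough to support them.
- Show the 3-year value with its number at risk.

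**Cost.** SAP wording and minor programming, with no new data. The recorded-duration table will understate the true length of events still open; the censored time-to-resolution analysis covers this for first onsets. Two survival rows are lost.
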